DEFINITION OF TREATMENT FAILURE	Treatment failure is defined as the presence of diarrhea (passage of ≥ 3 watery stools per 24-hour period for two consecutive days) and C. difficile toxin A/B positive stool within 60 days of FMT treatment plus receipt of anti- C. difficile antibiotics.
STUDY AGENT, DOSE OF ADMINISTRATION	
Processed intestinal bacteria from a screened healthy donor will be administered lyophilized FMT to be given by the oral route. FMT will be given as follows:
 
 1. Group 1: With bowel prep and Imodium 1st treatment day, lyophilized product generated from 50g of stool 2nd treatment day, lyophilized product generated from 50g of stool 2. Group 2: With bowel prep and Imodium 1st treatment day, lyophilized product generated from 100g of stool 2nd treatment day, lyophilized product generated from 50g of stool 3. Group 3: With bowel prep and Imodium 1st treatment day, lyophilized product generated from 100g of stool 2nd treatment day, lyophilized product generated from 100g of stool 4. Unblinded Group 4: (Without bowel prep and Imodium) 1st treatment day, lyophilized product generated from 100g of stool 2nd treatment day, lyophilized product generated from 100g of stool
EFFICACY EVALUATION	
Primary Endpoint:
 
 • Safety of FMT (lyophilized capsules with various doses) • Prevention of subsequent bouts of CDI in 60 days post FMT. • Safety of FMT (lyophilized capsules with same doses) without using pre-FMT bowel preparation and Imodium • Prevention of subsequent bouts of CDI in 60 days post FMT without using pre-FMT bowel preparation and Imodium. 
Secondary Endpoint:
 
 • To characterize improvement in microbiota diversity from baseline in subjects treated with various doses of lyophilized capsules.

SAFETY EVALUATION	To ensure safe study conduct during the study, an independent, non-blinded, external Data and Safety Monitoring Board (DSMB) will be established to perform safety evaluations on an ongoing basis. A DSMB charter will be developed and will detail the review of the safety data. The DSMB will have the power to stop the trial.
STUDY STOPPING RULES	Study may be halted or discontinued if the DSMB identifies a trend of more illnesses or side effects in one or more of the treatment groups.

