2. OBJECTIVE

Primary endpoints of the study are to evaluate the safety of lyophilized product by capsules with various doses and the prevention of subsequent bouts of CDI in 60 days post FMT; and to evaluate the safety of lyophilized product by capsules with same doses without bowel preparation and Imodium, and the prevention of subsequent bouts of CDI in 60 days post FMT without bowel preparation and Imodium. The secondary endpoint is to characterize improvement in microbiota diversity from baseline in subjects treated with various doses of lyophilized capsules.

Lyophilized FMT intestinal bacteria inoculate from well-screened healthy volunteer donors providing ≥ 100 grams of stool/FMT will be generated. Donor intestinal bacteria suspensions will be diluted (1:5 dilution) ≥ 500 mL for later lyophilization and encapsulation. Fecal samples from donors and recipients will be saved for future studies (e.g. microbiome analysis).

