10.2 Statistical Methods

10.2.1 General Considerations

All analyses will be performed, and all tables, figures, and data listings will be prepared using SAS (Cary, NC). Summary statistics for continuous variables will include the mean, standard deviation, median, minimum, and maximum value; categorical variables will be presented as counts and percentages. For all analyses, baseline is defined as the date of fecal transplantation.

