10.2.2 Power Calculations

Assuming recipients receiving 100g for both treatment days, 100g on the first treatment day and 50g on the second treatment, or 50g for both treatment days, or 100g for both treatment days without bowel prep and Imodium has 88%, 80%, 70% and 80% efficacy in preventing post RCDI respectively, it is determined that 348 recipients (1:1:1:1 ratio) would provide 85% power to detect a statistically significant difference in the distributions of efficacy between the 4 treatment groups at the two-sided $\alpha = 0.05$ level of significance. Assuming 10% of patients would be lost to follow-up, 360 (90 in each group) recipients are planned.

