10.2.3 Analysis Populations

Two primary analyses will be performed:

- 1) Analysis for safety and efficacy between three groups (1-3) receiving varied doses of lyophilized product generated from stool (50g for both treatment days; 100g on the first treatment day and 50g on the second treatment; 100g for both treatment days)
- 2) Analysis for safety and efficacy between two groups (3 and 4) with and without bowel preparation and Imodium receiving same high doses of lyophilized product (100g for both treatment days).

- All analyses will be conducted using the intent-to-treat population. Intent-to-treat is defined as all subjects who have started the procedure.
- Listings and summary tables with descriptive statistics will be prepared for demographic data (gender, date of birth, race/ethnicity), and medical history data.

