10.2.5 Analyses of Safety

All adverse events and serious adverse events will be coded using the Medical Dictionary for Regulatory Activities Version 12.0, which is a registered trademark of the International Federation of Pharmaceutical Manufacturers and Associations. The number and percentage of subjects reporting at least one occurrence of an adverse event and/or serious adverse event for each system organ class and preferred term will be tabulated. Term will also be tabulated by severity and by the relationship to the procedure. For multiple occurrences of the same adverse event with different severities, the adverse event with the highest severity will be tabulated. For multiple occurrences of the same adverse event with different relationships to the procedure (related and not related); the adverse event will be tabulated as related. All adverse events and or serious adverse events for all subjects will be presented in data listings. Narratives will also be prepared for each serious adverse event.

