10.2.6 Efficacy Analyses

While we will perform standard statistical analyses as outlined above, we do not expect to achieve statistical significance only trends.

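### Safety between groups is a primary comparison, but the plan gives no overall safety measure, between-group difference or interval, so it cannot say how much excess harm the trial has excluded

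*Combined protocol and SAP*

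**What the plan says.** Safety is a primary endpoint throughout. Section 2 opens with "Primary endpoints of the study are to evaluate the safety of lyophilized product by capsules with various doses". The Synopsis (Efficacy Evaluation) lists as a further primary endpoint "Safety of FMT (lyophilized capsules with same doses) without using pre-FMT bowel preparation and Imodium". Section 10.2.3 then sets two primary analyses, both comparative: "Analysis for safety and efficacy between three groups (1-3) receiving varied doses of lyophilized product generated from stool", and "Analysis for safety and efficacy between two groups (3 and 4) with and without bowel preparation and Imodium".

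The method for these comparisons is in 10.2.5: "The number and percentage of subjects reporting at least one occurrence of an adverse event and/or serious adverse event for each system organ class", the same by preferred term, tabulation by severity and relationship, listings, and a narrative for each SAE. That section does not say that the tables are split by treatment group. The general rule in 10.2.1 is "categorical variables will be presented as counts and percentages". The only reference to further inference is in 10.2.6, under efficacy: "While we will perform standard statistical analyses as outlined above, we do not expect to achieve statistical significance only trends". No test is set out above that sentence. The sample size in 10.2.2 rests on efficacy rates alone.

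**The concern.** A primary comparison needs a quantity that compares the groups and a statement of its uncertainty. For safety the plan has neither. Spreading events over system organ classes and preferred terms leaves few events per row, and nothing brings them together into one measure per group.

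At stake is half of the primary question. At the end of the trial the investigators could say how many subjects in each group had each event. They could not say, from the planned analysis, how much extra risk has been excluded for the highest dose or for omitting bowel preparation and Imodium.

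**Working it through.** **Plan's own figure.** There is none for safety: no expected event rate, margin, power or interval width. The 85% power in 10.2.2 is for efficacy and does not bear on this point.

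**Inputs from the plan.**
- 90 per group: "Assuming 10% of patients would be lost to follow-up, 360 (90 in each group) recipients are planned" (10.2.2).
- Two-sided 0.05, stated in 10.2.2 for efficacy and borrowed here.
- Analysis set: everyone who started the procedure (10.2.3). Subjects who leave before the Day 1 dose do not count towards the randomized total (4.4), so 90 is the right denominator.

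**Assumption.** The baseline SAE rate is not in the documents. Baselines of 5% to 20% are used, each compared with its double.

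**Step 1: chance of missing a doubling.** Power comes from exact enumeration of two binomials with n = 90, rejecting when the pooled chi-square test gives p < 0.05. The chance of a miss is 1 minus power. Fisher's exact test is shown as a check.

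| Assumed rates | Power, chi-square | Missed | Missed, Fisher |
|---|---|---|---|
| 5% vs 10% | 24.0% | 76% | 83% |
| 10% vs 20% | 46.9% | 53% | 60% |
| 15% vs 30% | 67.9% | 32% | 38% |
| 20% vs 40% | 84.2% | 16% | 20% |

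Hand check of the 10% vs 20% row by the normal approximation:
- mean rate 0.15; null SE = sqrt(2 × 0.15 × 0.85 / 90) = 0.0532; 1.96 × 0.0532 = 0.1043
- alternative SE = sqrt((0.10 × 0.90 + 0.20 × 0.80) / 90) = 0.0527
- power = Φ((0.10 − 0.1043) / 0.0527) = Φ(−0.08) = 47%

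Power reaches 50% at a baseline of about 11% (just over 12% by Fisher). Below that a doubling is missed more often than not; above it, it is not.

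**Step 2: what equal counts would exclude.** The Newcombe 95% upper limit for a risk difference of zero is sqrt((u − p)² + (p − l)²), where l and u are the Wilson limits for one group.

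| Events per group | p | Wilson limits | Upper limit of difference | Relative to p |
|---|---|---|---|---|
| 5/90 | 5.6% | 2.4% to 12.4% | +7.5 points | 7.5 / 5.6 = 1.3 |
| 9/90 | 10.0% | 5.4% to 17.9% | +9.2 points | 9.2 / 10 = 0.92 |
| 18/90 | 20.0% | 13.0% to 29.4% | +11.7 points | 11.7 / 20 = 0.59 |

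So identical counts still allow an excess larger than the baseline itself at 5/90, and nearly as large at 9/90. The tables in 10.2.5 would show none of this.

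**Step 3: would a crude percentage to Day 180-200 be enough?** Three provisions say it needs care.
- Section 6 stops clinical follow-up of treatment failures and withdraws retreated subjects after the retreatment Day 2 call. If failure differs by group, so does time at risk.
- Section 9.1.1 makes a CDI recurrence needing hospitalization of 24 hours or more an SAE, so an SAE measure mixes efficacy failure with harm.
- Section 9.5 leaves expected mild to moderate diarrhea from bowel preparation and mild constipation from Imodium unrecorded in groups 1-3. A measure of any adverse event would therefore not be like for like between groups 3 and 4. SAEs and Grade 3 or higher events are less exposed to this.

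**The case against.** Descriptive safety tables are normal in a Phase II dose-ranging trial, and the plan never proposes a safety test, so low power for one may look beside the point. Safety is also judged in other ways: the investigator's causality assessment (9.3.2), SAE narratives (10.2.5), an unblinded DSMB that may act on a trend between groups (Synopsis), halting after a possibly related SAE (9.10), and a final DSMB report on drug-related events (9.6).

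Much of this stands. These are real routes to a safety judgment. But none yields an estimate of the difference between groups, and the trend that the DSMB may act on is undefined. Descriptive tables suffice where safety is supportive; here 10.2.3 names the safety comparison as primary. The power figures show only what this sample size can resolve, and the proposed change reports that precision without improving it.

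Three stronger readings are tempting, and the documents do not support them.
- A reader might infer that the plan treats no visible difference as proof of safety. It states no such rule; it sets no criterion in either direction.
- A reader might infer that the trial would usually miss a doubling of serious events. That holds only below a baseline of about 11-12%. Hospitalization of 24 hours or more counts as serious and follow-up runs 180-200 days, so a higher rate cannot be excluded.
- A reader might cut the groups to 81 (90 × 0.9) for the 10% loss. That allowance belongs to the efficacy sizing. Subjects lost later stay in the analysis set with the events recorded before loss.

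**Conclusion.** The point holds as a gap in the analysis of a primary endpoint. With counts and percentages alone, the trial cannot say how much excess harm it has excluded for dose or for omitting bowel preparation and Imodium. That conclusion rests on the text and does not depend on any event rate.

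Its size does depend on an assumed rate: at 90 per group a doubling would be missed between 76% of the time (5% baseline) and 16% (20% baseline), and equal counts leave upper limits between about +7.5 and +11.7 points. The change should be made: it is cheap and uses data already planned. It does not imply that the trial is too small or that any group is unsafe.

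**What to change.** In 10.2.5:
1. State that safety tables are presented by treatment group.
2. Name one overall measure from data already collected, for example subjects with at least one SAE or Grade 3 or higher adverse event, counted from the first dose over a common window.
3. For 1 vs 3, 2 vs 3 and 4 vs 3, report the risk difference with a 95% score interval (Newcombe or Miettinen-Nurminen).
4. Word the safety conclusion from the upper limit, as the excess risk that has been excluded, and state that a non-significant difference is not evidence of equal safety.
5. Because failures and retreated subjects leave follow-up early, use a time-to-first-event (Kaplan-Meier) risk difference or exposure-adjusted rates, as the main or a sensitivity analysis. Say that censoring at departure assumes later risk like that of subjects who remain.
6. Show the measure with and without hospitalized CDI recurrence.
7. Keep the system organ class and preferred term tables as supporting description.

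The cost is a few lines in 10.2.5 and one or two more tables, with no new data or patients. The downside is that wide intervals will make the safety conclusion look less firm.

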10.2.6 Efficacy Analyses

While we will perform standard statistical analyses as outlined above, we do not expect to achieve statistical significance only trends.

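### The 85% power in 10.2.2 belongs to a four-group comparison that is not a primary analysis and reaches only about 70%; no efficacy test is named for either primary analysis, and 10.2.6 disclaims significance

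*Combined protocol and SAP*

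**What the plan says.** Four parts of section 10.2 of the combined protocol and SAP bear on the efficacy test.

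- **10.2.2 Power Calculations** assumes that groups 3, 2, 1 and 4, in that order, "has 88%, 80%, 70% and 80% efficacy in preventing post RCDI respectively". It concludes that 348 recipients "would provide 85% power to detect a statistically significant difference in the distributions of efficacy between the 4 treatment groups", two-sided at 0.05. On loss it says: "Assuming 10% of patients would be lost to follow-up, 360 (90 in each group) recipients are planned".
- **10.2.3 Analysis Populations** lists two primary analyses. The first is "Analysis for safety and efficacy between three groups (1-3) receiving varied doses of lyophilized product generated from stool". The second compares groups 3 and 4, which receive the same dose with and without bowel preparation and Imodium. Neither has a named test.
- **10.2.4 Randomization Procedures** calls 360 the number of evaluable subjects.
- **10.2.6 Efficacy Analyses** consists of one sentence: "While we will perform standard statistical analyses as outlined above, we do not expect to achieve statistical significance only trends".

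Sections 10.2.1 to 10.2.5 cover summary statistics, power, populations, randomization and adverse event tables. None of them describes an efficacy test to which 10.2.6 could refer.

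**The concern.** The sample size is tied to a hypothesis that is neither primary analysis. The four-group comparison mixes the dose question with the bowel preparation question. A rejection would not say which of the two produced it.

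Sections 10.2.2 and 10.2.6 also cannot both stand. A trial with 85% power under its own assumptions should expect significance.

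With no named test and no decision rule, the efficacy test can be chosen after the data are seen, and 10.2.6 announces in advance that non-significant tendencies will be reported. This matters most for dose. Groups 1-3 are ordered by total stool equivalent (100, 150 and 200 g) and by assumed efficacy (70%, 80%, 88%), yet nothing in the plan uses that order.

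**Working it through.** **Inputs.** Efficacy is 0.70, 0.80, 0.88 and 0.80 for groups 1 to 4, and alpha is 0.05 two-sided (both 10.2.2). Three sizes per group are relevant:
- 348/4 = 87, the powered number
- 360/4 = 90, the planned number, called evaluable in 10.2.4
- 90 × 0.9 = 81, the planned number after the 10% loss

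**1. The plan's own figure: four groups, 3 df.** The noncentrality is λ = n Σ(pᵢ − p̄)² / [p̄(1 − p̄)].
- p̄ = 3.18/4 = 0.795, so p̄(1 − p̄) = 0.162975.
- Σ(pᵢ − p̄)² = 0.009025 + 0.000025 + 0.007225 + 0.000025 = 0.0163.
- At n = 87, λ = 87 × 0.0163/0.162975 = 8.70, which gives **69.5%** power (69.7% simulated).

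The 85% is not reproduced. The likelihood-ratio, arcsine and unpooled Wald versions give 69.9%, 70.5% and 72.0%; alpha 0.10 gives 79.6%. Power of 85% would need 123 per group, 492 in total. A pairwise test of 0.88 versus 0.70 with unpooled variance does match: (1.960 + 1.036)² × (0.1056 + 0.21)/0.18² = 87.5 per group, or 84.8% at 87. That may be where 348 came from, but the document does not say so.

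**2. Groups 1-3, order ignored, 2 df.** p̄ = 2.38/3 = 0.7933, p̄(1 − p̄) = 0.16396 and Σ(pᵢ − p̄)² = 0.016267. At n = 87, λ = 8.63 and power is 75.2% (76.0% simulated).

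**3. Groups 1-3, Cochran-Armitage trend test, 1 df.** With equal groups and scores −1, 0, 1 for 100, 150, 200 g:
- Expected numerator: n(0.88 − 0.70) = 15.66 at n = 87.
- Null variance: 2n p̄(1 − p̄) = 28.53. Alternative variance: n(0.21 + 0.1056) = 27.46.
- Power = Φ[(15.66 − 1.96 × 5.341)/5.240] = Φ(0.991) = **83.9%** (84.4% simulated).
- Simulated type I error is 5.0%.

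**4. Group 3 versus 4.** With 0.88 versus 0.80 at n = 87, the null standard error is √(2 × 0.84 × 0.16/87) = 0.0556 and the alternative is √[(0.1056 + 0.16)/87] = 0.0553. Power = Φ[(0.08 − 1.96 × 0.0556)/0.0553] = 30%. The 95% CI half-width is 1.96 × 0.0553 = 10.8 points.

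**Power by size (formula / simulation)**

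| Per group | Four groups, 3 df | Groups 1-3, 2 df | Groups 1-3, trend | Group 3 vs 4 |
|---|---|---|---|---|
| 81 | 66.0 / 66.3% | 72.0 / 72.8% | 81.2 / 81.7% | 28.3 / 28.0% |
| 87 | 69.5 / 69.7% | 75.2 / 76.0% | 83.9 / 84.4% | 30.0 / 29.6% |
| 90 | 71.1 / 71.6% | 76.7 / 77.5% | 85.1 / 85.8% | 30.9 / 30.7% |

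**5. Alpha.** The plan states no rule for its two primary analyses. With an assumed split to 0.025, simulated trend power is 73% at 81, 77% at 87 and 78% at 90 per group.

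**6. Other dose-response shapes (87 per group, simulated)**

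| Groups 1 / 2 / 3 | Trend | 2 df |
|---|---|---|
| 70 / 85 / 80% | 37% | 58% |
| 70 / 88 / 80% | 38% | 76% |
| 70 / 80 / 80% | 35% | 34% |
| 70 / 70 / 88% | 82% | 87% |
| 70 / 88 / 88% | 87% | 89% |

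**The case against.** **The plan never chose an unordered test.** A reader might infer from 10.2.2 and 10.2.3 that it chose an inferior one. The documents do not support that: the wording carries no ordering, but no test is named. The defect is that the test is missing.

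**The trend test does not settle the dose question.** With equal groups and equally spaced scores, its numerator is simply group 3 successes minus group 1 successes; group 2 enters only through the variance. A plain group 1 versus 3 test has practically the same power, 84.4% at 87 per group. A significant trend would not show where the middle schedule lies. This stands, and it is why the test needs group-wise estimates beside it.

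**The advantage rests on the assumed shape.** This also stands, as the last table shows. Against it, the rising 70/80/88% pattern is the plan's own assumption. Preferring a trend test is a judgement; naming some test is not optional.

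**A trend test does not simply rescue the stated 85%.** That reading needs 90 analysed per group and the full 0.05. Loss of 10% gives about 82%. Sections 4.8 and 7.3 also remove subjects who take systemic antibiotics within 60 days from efficacy, at a rate the plan does not give.

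**The 10.2.6 disclaimer is partly right.** At about 30% power, significance should indeed not be expected for group 3 versus 4. As written, however, the sentence covers all efficacy analyses.

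**Conclusion.** The point holds. The 85% is attached to a comparison that is not primary and is overstated by about 15 points for that comparison (about 70% at 87 per group). Neither primary analysis has a named efficacy test or its own power statement, and 10.2.6 contradicts 10.2.2.

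Under the assumed rates, a dose-trend test on groups 1-3 gains about 8-9 points over an unordered test with no extra patients: about 84% at 87, 85-86% at 90 and 82% at 81 per group. These figures assume a monotone, near-linear response and the full two-sided 0.05. Group 3 versus 4 stays at 28-31% whichever test is chosen for dose.

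The missing test and the contradiction are the firm part. The trend test is the recommended way to fill the gap, not the only defensible one. A reader might also take the word for tendencies in 10.2.6 as a planned dose-trend test. The sentence sets it against statistical significance, so non-significant tendencies are the natural reading.

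**What to change.** 1. **10.2.2:** withdraw the 85% figure for four groups. State power for each primary analysis at two-sided 0.05: dose trend about 84% at 87 per group and 82% at 81 (after 10% loss); group 3 versus 4 about 30%.
2. **10.2.3 and 10.2.6:** name the two-sided Cochran-Armitage trend test (scores 100, 150, 200 g) as the primary efficacy test for groups 1-3. Support it with the 2-df chi-square, cure rates by group, and pairwise risk differences with 95% CIs, so that the middle schedule is described.
3. **Alpha:** state how it is handled over the two primary analyses, and restate trend power if it is split.
4. **10.2.6:** replace the disclaimer. Say that only group 3 versus 4 is underpowered, that it will be reported as a risk difference with 95% CI (half-width about 11 points), and that non-significance will not be read as showing bowel preparation and Imodium to be unnecessary.

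The cost is protocol wording only. The statistical price is lower power if response is not monotone and about 2-5 points for step shapes; at a 70/80/80% plateau the trend test gains nothing.
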